6.5. Dose Modification

No dose modifications will be allowed.

6.6. Intervention after the End of the Study

There will be no intervention offered at the end of the study.

DISCONTINUATION OF STUDY INTERVENTION AND 7. PARTICIPANT DISCONTINUATION/WITHDRAWAL

7.1. **Discontinuation of Study Intervention**

In rare instances, it may be necessary for a participant to permanently discontinue (definitive discontinuation) study intervention. If study intervention is definitively discontinued, the participant will remain in the study to be evaluated for efficacy and safety, unless consent is withdrawn. See the SoA (Section 1.3) for data to be collected at the time of discontinuation of study intervention and follow-up and for any further evaluations that need to be completed.

[figure not shown]
7.1.1. **Liver Chemistry Stopping Criteria**

Liver chemistry stopping, and increased monitoring criteria have been designed to assure participant safety and evaluate liver event etiology.

Discontinuation of study intervention for abnormal liver tests is required when:

- a participant meets one of the conditions outlined in the algorithm
- when in the presence of abnormal liver chemistries not meeting protocol-specified stopping rules, the Investigator believes study intervention discontinuation is in the best interest of the participant.

Phase 2 Liver Chemistry Stopping and Increased Monitoring Algorithm

INR>1.5*

*INR value not applicable to participants on anticoagulants

Abbreviations: ALT = alanine transaminase; INR = international normalized ratio; SAE = serious adverse event; ULN = upper limit of normal.

7.1.2. QTc Stopping Criteria

A participant with an average triplicate measurement meeting either of the bulleted criteria below will be withdrawn from the study:

- QTc >500 msec or uncorrected QT >600 msec
- Change from Baseline (Day 1 pre-dose) of QTc >60 msec

For participants with underlying bundle branch block, follow the discontinuation criteria below:

Day 1 pre-dose QTc with bundle branch block	Discontinuation QTc with bundle branch block
<450 msec	>500 msec
450-480 msec	≥530 msec

- The *Fridericia's* QT correction formula *must* be used for *each individual participant* to determine eligibility for and discontinuation from the study.
- The QTc should be based on the average of triplicate ECG readings obtained over a brief (e.g., 5-10 minute) recording period at Screening and at Day 1 (Baseline). At all other specified time points single ECGs are acceptable. However, if QTc prolongation (as defined in the same way as the withdrawal criteria) is detected, triplicate ECGs will be performed and the QTc must be based on the average of triplicated ECG readings.

7.1.3. Rechallenge

7.1.3.1. Study Intervention Restart or Rechallenge after liver stopping criteria

Study intervention restart or rechallenge after liver chemistry stopping criteria are met by any participant in this study is not allowed.

7.2. Participant Discontinuation/Withdrawal from the Study

- A participant may withdraw from the study at any time at his/her own request or may be withdrawn at any time at the discretion of the Investigator for safety, behavioral, compliance or administrative reasons. This is expected to be uncommon.
- A participant may be withdrawn from the study at any time if deemed to be demonstrating suspected, probable or confirmed COVID-19 infection. Specific details are in the SRM.
- At the time of discontinuing from the study, if possible, an early discontinuation visit should be conducted, as shown in the SoA (Section 1.3). See SoA (Section

- 1.3) for data to be collected at the time of study discontinuation and follow-up and for any further evaluations that need to be completed.
- If the participant withdraws consent for disclosure of future information, the sponsor may retain and continue to use any data collected before such a withdrawal of consent.
- If a participant withdraws from the study, he/she may request destruction of any samples taken and not tested, and the Investigator must document this in the site study records.

7.3. Lost to Follow-up

A participant will be considered lost to follow-up if he or she repeatedly fails to return for scheduled visits and is unable to be contacted by the study site.

The following actions must be taken if a participant fails to return to the clinic for a required study visit:

- The site must attempt to contact the participant and reschedule the missed visit as soon as possible and counsel the participant on the importance of maintaining the assigned visit schedule and ascertain whether or not the participant wishes to and/or should continue in the study.
- Before a participant is deemed lost to follow-up, the Investigator or designee must make every effort to regain contact with the participant (where possible, 3 telephone calls and, if necessary, a certified letter to the participant's last known mailing address or local equivalent methods). These contact attempts should be documented in the participant's medical record.
- Should the participant continue to be unreachable, he/she will be considered to have withdrawn from the study.

Discontinuation of specific sites or of the study as a whole are handled as part of Appendix 1.

8. STUDY ASSESSMENTS AND PROCEDURES

- Study procedures and their timing are summarized in the SoA (Section 1.3).
- Protocol waivers or exemptions are not allowed.
- Immediate safety concerns should be discussed with the sponsor immediately upon occurrence or awareness to determine if the participant should continue or discontinue study intervention.
- Adherence to the study design requirements, including those specified in the SoA (Section 1.3), is essential and required for study conduct.
- All Screening evaluations must be completed and reviewed to confirm that potential participants meet all eligibility criteria. The Investigator will maintain a Screening log to record details of all participants screened and to confirm eligibility or record reasons for Screening failure, as applicable.

• Procedures conducted as part of the participant's routine clinical management (e.g., blood count) and obtained before signing of ICF may be utilized for Screening or Baseline purposes provided the procedure met the protocol-specified criteria and was performed within the time frame defined in the SoA (Section 1.3).

CONFIDENTIAL

- The maximum amount of blood collected from each participant over the duration of the study, including any extra assessments that may be required, will not exceed 500 mL.
- Repeat or unscheduled samples may be taken for safety reasons or for technical issues with the samples.

8.1. Efficacy Assessments

8.1.1. Clinical Disease Assessments

8.1.1.1. Psoriasis Area Severity Index (PASI)

Psoriatic lesions will be assessed using the PASI scoring system [Fredriksson, 1978]. Erythema, induration, and scale are each graded on a 5-point scale (0-4), and the % BSA affected is scored on a 7-point scale (0-6) for each of the 4 specified body regions (head, upper extremities, trunk, and lower extremities). The body region scores are each multiplied by a weighted factor; and the sum of the region scores give the overall PASI score. Higher scores indicate more severe disease. PASI is a static measurement made without reference to a previous score (see SRM for full details).

The PASI assessment will be performed by the Investigator or suitably trained delegate, and whenever possible, the PASI assessments for an individual participant should be completed by the same assessor at all time points.

8.1.1.2. Psoriasis body Surface Area (BSA)

The BSA affected with psoriasis will be evaluated at all study visits by the Investigator or suitably trained delegate. In order to be eligible for the study, BSA must be $\geq 10\%$. As a reference, the area of the whole palm is counted as 1% BSA.

8.1.1.3. Static Investigator's Global Assessment of Disease Activity (sIGA)

The Investigator or physician designee only will complete a global assessment of disease activity using the physician global assessment item. A 5-point scoring system will be used to measure the severity of psoriatic lesions over the entire body at the time of evaluation (see SRM for full details).

Note:

- The Investigator or physician designee should complete the Investigator's global assessment independently of the participant.
- Ideally, the same Investigator or physician designee should perform all global assessments for each participant for the duration of the study.

8.2. Safety Assessments

Blinded safety data will be reviewed by the safety review team (SRT) details of which can be found in the SRT charter.

Planned time points for all safety assessments are provided in the SoA (Section 1.3).

8.2.1. Physical Examinations

- A complete physical examination will include, at a minimum, assessments of the head, eyes, ears, nose, throat, skin, thyroid, joint, lymph nodes, cardiovascular, respiratory, gastrointestinal and neurological systems. Height and weight will also be measured and recorded. Height will be measured at the screening visit only.
- A brief physical examination will include, at a minimum, weight and assessments of the skin, lungs, cardiovascular system, and abdomen (liver and spleen).
- Investigators should pay special attention to clinical signs related to previous serious illnesses or that could be related to infection (e.g. COVID-19).
- At each visit, the participant should be asked whether they have had COVID-19 symptoms, or exposure to anyone with COVID-19 positive test in the past 14 days. These symptoms include, but are not limited to, a high temperature and dry cough. Guidance on how to manage participants who develop COVID-19 symptoms during the study are described in the SRM. Participants with exposure to anyone with COVID-19 infection should not be included in the study until 14 days after the last exposure.

8.2.2. Vital Signs

 Vital signs will be measured in a semi-supine position after 5 minutes rest and will include temperature, systolic and diastolic blood pressure, pulse and respiratory rate.

8.2.3. Electrocardiograms

- Triplicate and single 12-lead ECGs will be obtained as outlined in the SoA (see Section 1.3) using an ECG machine that automatically calculates the heart rate and measures PR, QRS, QT, and QTc intervals. Refer to Section 7 for QTc withdrawal criteria and additional QTc readings that may be necessary.
- At each time point at which triplicate ECG are required (Screening and Day 1 [Baseline]), 3 individual ECG tracings should be obtained as closely as possible in succession, but no more than 2 minutes apart. The full set of triplicates should be completed over a brief (e.g., 5-10 minutes) recording period.

8.2.4. Clinical Safety Laboratory Assessments

• Refer to Appendix 2 for the list of clinical laboratory tests to be performed and to the SoA (Section 1.3) for the timing and frequency.

- The Investigator must review the laboratory report, document this review, and record any clinically relevant changes occurring during the study in the AE section of the CRF. The laboratory reports must be filed with the source documents. Clinically significant abnormal laboratory findings are those which are not associated with the underlying disease, unless judged by the Investigator to be more severe than expected for the participant's condition.
- All laboratory tests with values considered clinically significantly abnormal during participation in the study should be repeated until the values return to normal or Baseline or are no longer considered significantly abnormal by the Investigator or medical monitor.
- If such values do not return to normal/Baseline within a period of time judged reasonable by the Investigator, the etiology should be identified and the sponsor notified.
- All protocol-required laboratory assessments, as defined in Appendix 2, must be conducted in accordance with the laboratory manual and the SoA (Section 1.3).

8.2.5. Suicidal Ideation and Behaviour Risk Monitoring

GSK2982772 is considered to be a CNS-active drug. There has been some concern that some CNS-active drugs may be associated with an increased risk of suicidal thinking or behaviour when given to some patients with PsO. Although this drug has not been shown to be associated with an increased risk of suicidal thinking or behaviour when given to healthy volunteers, GSK considers it important to monitor for such events before or during clinical studies with compounds such as this.

Families and caregivers of participants being treated with GSK2982772 should be alerted regarding the need to monitor participants for the emergence of unusual changes in behaviour, as well as the emergence of suicidal ideation and behaviour and to report such symptoms immediately to the study Investigator.

Participants being treated with GSK2982772 must be monitored appropriately for suicidal ideation and behaviour or any other unusual changes in behaviour. Participants that experience signs of suicidal ideation or behavior must be withdrawn from study treatment.

At Screening, the 'Baseline/Screening C-SSRS' will be completed. At each subsequent study visit, the 'Since Last Visit C-SSRS' will be completed. GSK Version 4.1 of both rating scales will be used.

Participants who answer 'yes' to any suicidal behaviour or 'yes' to suicidal ideation Questions 4 or 5 will be referred to their general practitioner (GP) or appropriate psychiatric care. The medical monitor will be notified. If appropriate, an AE or SAE must be reported (see Section 8.3- AE and SAE). In addition, the Investigator must complete a Possible Suicidality Related Adverse Event (PSRAE) form to collect detailed information on the circumstances of the reported AEs which, in the Investigator's opinion, are

possibly suicidality-related. These may include, but are not limited to, an event involving suicidal ideation, a preparatory act toward imminent suicidal behaviour, a suicide attempt, or a completed suicide.

8.3. Adverse Events and Serious Adverse Events

The definitions of an AE or SAE can be found in Appendix 3.

AEs will be reported by the participant (or, when appropriate, by a caregiver, surrogate, or the participant's legally authorized representative) to the site staff.

The Investigator and any qualified designees are responsible for detecting, documenting, and reporting events that meet the definition of an AE or SAE and remain responsible for following up AEs that are serious, considered related to the study intervention or the study, or that caused the participant to discontinue the study (see Section 7).

8.3.1. Time Period and Frequency for Collecting AE and SAE Information

- All SAEs will be collected from the signing of the informed consent until the follow-up visit at the time points specified in the SoA (Section 1.3).
- All AEs will be collected from the start of intervention until the follow-up visit at the time points specified in the SoA (Section 1.3).
- Medical occurrences that begin before the start of study intervention but after obtaining informed consent will be recorded on the Medical History/Current Medical Conditions section of the CRF not the AE section.
- All SAEs will be recorded and reported to the sponsor or designee immediately and under no circumstance should this exceed 24 hours, as indicated in Appendix 3. The Investigator will submit any updated SAE data to the sponsor within 24 hours of it being available.
- Investigators are not obligated to actively seek AEs or SAEs after the conclusion of the study participation. However, if the Investigator learns of any SAE, including a death, at any time after a participant has been discharged from the study, and he/she considers the event to be reasonably related to the study intervention or study participation, the Investigator must promptly notify the sponsor.

8.3.2. Method of Detecting AEs and SAEs

- The method of recording, evaluating, and assessing causality of AEs and SAEs and the procedures for completing and transmitting SAE reports are provided in Appendix 3.
- Care will be taken not to introduce bias when detecting AE and/or SAE. Openended and non-leading verbal questioning of the participant is the preferred method to inquire about AE occurrence.

8.3.3. Follow-up of AEs and SAEs

After the initial AE/SAE report, the Investigator is required to proactively follow each participant at subsequent visits/contacts. All SAEs will be followed until the event is resolved, stabilized, otherwise explained, or the participant is lost to follow-up (as defined in Section 7.3). Further information on follow-up procedures is given in Appendix 3.

8.3.4. Regulatory Reporting Requirements for SAEs

- Prompt notification by the Investigator to the sponsor of a SAE is essential so that legal obligations and ethical responsibilities towards the safety of participants and the safety of a study intervention under clinical investigation are met.
- The sponsor has a legal responsibility to notify both the local regulatory authority and other regulatory agencies about the safety of a study intervention under clinical investigation. The sponsor will comply with country-specific regulatory requirements relating to safety reporting to the regulatory authority, Institutional Review Boards (IRB)/Independent Ethics Committees (IEC), and Investigators.
- For all studies except those utilizing medical devices Investigator safety reports
 must be prepared for suspected unexpected serious adverse reactions (SUSAR)
 according to local regulatory requirements and sponsor policy and forwarded to
 Investigators as necessary.
- An Investigator who receives an Investigator safety report describing a SAE or other specific safety information e.g., summary or listing of SAEs) from the sponsor will review and then file it along with the IB and will notify the IRB/IEC, if appropriate according to local requirements.

8.3.5. Pregnancy

- Details of all pregnancies in female participants and, if indicated, female partners of male participants will be collected after the start of study intervention and until 30 days after the last dose.
- If a pregnancy is reported, the Investigator must inform GSK within 24 hours of learning of the pregnancy and must follow the procedures outlined in Appendix 4.
- Abnormal pregnancy outcomes (e.g., spontaneous abortion, fetal death, stillbirth, congenital anomalies, ectopic pregnancy) are considered SAE.

8.3.6. Cardiovascular and Death Events

For any cardiovascular events detailed in Appendix 3 and all deaths, whether or not they are considered SAEs, specific Cardiovascular (CV) and Death sections of the CRF will

be required to be completed. These sections include questions regarding cardiovascular (including sudden cardiac death) and non-cardiovascular death.

The CV CRFs are presented as queries in response to reporting of certain CV medical dictionary for regulatory activities (MedDRA) terms. The CV information should be recorded in the specific cardiovascular section of the CRF within one week of receipt of a CV Event data query prompting its completion.

The Death CRF is provided immediately after the occurrence or outcome of death is reported. Initial and follow-up reports regarding death must be completed within one week of when the death is reported.

8.4. Treatment of Overdose

For this study, any dose of GSK2982772 greater than 960 mg within a 20-hour time period will be considered an overdose.

GSK does not recommend specific treatment for an overdose.

In the event of an overdose, the Investigator/treating physician should:

- 1. Contact the Medical Monitor immediately.
- 2. Closely monitor the participant for AE/SAE and laboratory abnormalities until GSK2982772 can no longer be detected systemically (at least 2 days).
- 3. Obtain a plasma sample for PK analysis within 1 day from the date of the last dose of study intervention if requested by the Medical Monitor in conjunction with clinical pharmacologist (determined on a case-by-case basis).
- 4. Document the quantity of the excess dose as well as the duration of the overdosing in the CRF.

Decisions regarding dose interruptions or modifications will be made by the Investigator in consultation with the Medical Monitor based on the clinical evaluation of the participant.

8.5. Pharmacokinetics

8.5.1. Blood Sample Collection

Blood samples for PK analysis of GSK2982772 will be collected prior to dosing at the time points indicated in SoA, Section 1.3. The actual date and time (24-hour clock) of each blood sample collection will be recorded. Details of blood sample collection, processing, storage and shipping procedures are provided in the SRM.

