- 2. For women of child-bearing potential only: Serum pregnancy test must be performed at Screening. At all other visits other than Week 2, a urine pregnancy test will be performed.

 If a urine test result is positive or ambiguous, a confirmatory serum test must be performed.
- 3. Perform pre-dose during treatment period (NB excludes Week 12/Day 85 visit as Day 84 is the last day of dosing).
- 4. Triplicate ECGs will be taken at Screening and on Day 1 (Baseline). At all other specified time points single ECGs are acceptable. However, if QTc prolongation is detected triplicate ECGs should be performed. Fridericia's formula (QTcF) must be used for the QTc correction.
- 5. Blood pressure (systolic and diastolic), heart rate, respiratory rate and temperature to be assessed at all time points, as well as COVID-19 symptoms check.
- 6. Urinalysis not required on Days 29 and 57.
- 7. Blood samples will be taken after overnight fast for fasting lipid, glucose and insulin analysis.
- 8. Following Day 1, participants will take study medication at home. At the Week 2, 4, and 8 visits, the dose should not be taken before the clinic visit. Instead, the dose should be taken either on site, after all pre-dose study assessments have been completed (preferred), or after the visit (at home) if the timing of the on-site dosing would result in the dose being less than 20 hours after the last dose (i.e. overdose). There is no dose administered at Week 12/Day 85.
- 9. PGx sample collected at Day 1, after randomization and if the participant provides additional, optional informed consent. If sample is not collected at Day 1, it can be collected at any time post-randomization.
- 10. Mandatory skin biopsy samples will be collected from all participants: one non-lesional and one lesional biopsy will be collected on Day 1 (Baseline) before 1st dose of study medication. One additional lesional biopsy sample from the same plaque will be collected pre-dose at Week 12/Day 85.
- 11. One optional lesional skin biopsy sample will also be collected at Week 4/Day 29 from consenting participants only. A separate consent must be obtained.

- 12. Collection of 1 lesional skin biopsy sample required at Early Withdrawal visit if study withdrawal occurs prior to Week 12 and if the participant has completed at least 14 days of treatment. If biopsy has already been obtained within the last 14 days, then another biopsy will not be collected.

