6.2. Measures to Minimize Bias: Randomisation and Blinding

Randomisation

At Screening, a unique Participant Number will be assigned to any participant who has at least one Screening procedure performed, other than informed consent. The unique Participant Number will be used to identify individual participants during the course of the study.

Participants who meet Screening eligibility criteria will be randomised to a treatment group through an Interactive Web Response System (IWRS). Before the study is initiated, the log in information & directions for the IWRS will be provided to each site. The IWRS will confirm the participant's case report form (CRF) number (Participant Number) and provide the randomisation number, where:

• A randomisation number will be assigned from a randomisation schedule generated by Clinical Statistics, prior to the start of the study, using validated internal software.

Once assigned, this number must not be reassigned to any other participant in the study. The randomisation is centrally controlled by the IWRS.

Participants will be randomised to receive either GSK2982772 or placebo in a 2:1 ratio. The randomisation will be stratified by prior biologic use. Participants will take study medication every day, once a day for 12 weeks, at approximately the same time each day.

Participants will be administered the first daily dose of study medication by site staff during the site visit for Day 1 (Week 0). At subsequent visits, the dose should be taken either on site (preferred) after the pre-dose assessments, or after the visit at home only if the participant dosing at site would result in a treatment overdose (refer to Section 8.4). Participants will self-administer all other doses of study medication and will record the date and time in the diary cards provided to them. Returned study intervention should not be re-dispensed to the participants.

See the SRM for further details.

Blinding

This will be a double-blind study.

Access to participant-level unblinded data will be restricted to the GSK Biostatistics and CPMS members of the study team for the purpose of conducting analyses for the planned interim analysis. Summary-level data will be shared with the internal DRC at the interim analysis, membership of which will be listed in a data review charter. Results of the interim will not be shared outside of this committee, only the decision and its

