6.3. Study Intervention Compliance

- When participants are dosed at the site, they will receive study intervention directly from the Investigator or designee, under medical supervision. The date and time of each dose administered in the clinic will be recorded in the source documents. The dose of study intervention and study participant identification will be confirmed at the time of dosing by a member of the study site staff other than the person administering the study intervention.
- If participants are not dosed at the site at the Week 2 (Day 15), Week 4 (Day 29) and/or Week 8 (Day 57) visit(s), the time the dose is taken on those visit days must be confirmed by the site staff through follow-up with the participant, and time and date of dose information will be recorded in the CRF.
- When participants self-administer study intervention(s) at home, compliance with study treatment will be assessed by reviewing the information from the returned diary cards at the study visits, and documenting compliance in the source documents and CRF.
- A record of the number of study treatment tablets dispensed to and taken by each
 participant must be maintained and reconciled with study intervention and
 compliance records. Intervention start and stop dates, including dates for intervention
 delays, will also be recorded in the CRF.

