- 4. Includes: Hepatitis A Immunoglobulin M (IgM) antibody; HbsAg and HBcAb; Hepatitis CRNA; Cytomegalovirus IgM antibody; Epstein-Barr viral capsid antigen IgM antibody (or if unavailable, obtain heterophile antibody or monospot testing); Hepatitis E IgM antibody
- 5. PK sample may not be required for participants known to be receiving placebo or non-GSK comparator interventions. Record the date/time of the PK blood sample draw and the date/time of the last dose of study intervention prior to pk blood sample draw on the CRF. If the date or time of the last dose is unclear, provide the participant's best approximation. If the date/time of the last dose cannot be approximated OR a PK sample cannot

be collected in the time period indicated above, do not obtain a PK sample. Instructions for sample handling and shipping are in the SRM.

Reference

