5.5. Pharmacokinetic

Pharmacokinetic analyses will be conducted using the PK population.

Pharmacokinetic blood samples will be collected pre-dose at Week 2 (Day 15), 4 (Day 29), 8 (Day 57) and 12 (Day 85) visits to measure trough plasma concentrations of GSK2982772. Skin biopsies will be taken pre-dose at Week 4 (Day 29) and Week 12 (Day 85) to measure trough concentrations of GSK2982772 in the skin.

Summaries of trough plasma and skin GSK2982772 concentrations by visit will be produced as well as for PK predicted target engagement (the formula for this derivation is provided in the OPS).

Line plots of individual participant trough plasma and skin concentrations by visit will be produced as well as a plot for the treatment group average by visit.

Scatter plot of trough skin concentration versus trough plasma concentration at Week 4 (Day 29) and Week 12 (Day 85) will be produced.

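### PK samples from visits that use the off-site dosing option are drawn less than 20 h after the previous dose, yet they are summarised as troughs with no check on time since dose

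*Protocol*

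**What the plan says.** **When the dose may move off site.** Footnote 8 to the treatment-period table in Protocol 1.3 prefers on-site dosing at Weeks 2, 4 and 8, after the pre-dose assessments. It allows home dosing after the visit "if the timing of the on-site dosing would result in the dose being less than 20 hours after the last dose". Section 6.2 repeats the condition: "after the visit at home only if the participant dosing at site would result in a treatment overdose". Section 8.4 supplies the threshold: "any dose of GSK2982772 greater than 960 mg within a 20-hour time period will be considered an overdose".

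**When the PK sample is drawn.** Footnote 3 to the same table makes the PK sample a pre-dose assessment. Section 8.5.1 says: "Blood samples for PK analysis of GSK2982772 will be collected prior to dosing at the time points indicated in SoA, Section 1.3". It also requires the actual draw time to be recorded. It gives no minimum time since the previous dose.

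**How the result is used.** The only PK endpoint (Protocol 3) is the trough concentration at Weeks 2, 4, 8 and 12. SAP 5.5 says the samples at these visits are taken "to measure trough plasma concentrations of GSK2982772". It feeds them into by-visit summaries and PK-predicted target engagement. SAP 5.5.1 uses trough concentration in plots against target engagement and, data permitting, in work relating it to PASI.

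**Which dose times are recorded.** When the participant is not dosed on site, Section 6.3 says "the time the dose is taken on those visit days must be confirmed by the site staff through follow-up with the participant", and that time goes into the CRF. Times of home doses go on diary cards (6.2), which are reviewed at visits (6.3). For liver-event PK samples, Appendix 6 note 5 makes a fuller CRF entry explicit: "Record the date/time of the PK blood sample draw and the date/time of the last dose of study intervention prior to pk blood sample draw".

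**The concern.** Being drawn before the next dose makes a sample a trough only if that dose falls at about the end of the dosing interval. The off-site option applies exactly when the visit comes too early for that. The rule that triggers home dosing therefore also identifies samples taken well before the interval ends, and nothing in the protocol or SAP separates them from true end-of-interval samples.

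The summary-of-changes table shows that off-site dosing at these visits came in with the current amendment. SAP version 2 is based on that protocol, but its version history lists no change for plasma sample timing.

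At stake is the one PK endpoint. The error runs one way: early samples overstate the trough. It also varies between participants with the clock time of their home dose, which adds noise to any trough-response relation in about 14 active participants. PK and predicted target-engagement summaries also go to the Data Review Committee at an interim that can be triggered by six active participants (SAP 5.8).

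**Working it through.** The plan gives no figure to reproduce. The check is one of ordering, followed by an illustration of size.

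**1. Ordering of times.** Measure hours from the previous dose. Let T be the PK draw and D the time at which an on-site dose would be given.
- The draw is a pre-dose assessment: T < D.
- Home dosing is allowed only if D < 20.
- Hence T < 20, and the shortfall against the once-daily interval is 24 − T > 4 h.

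This holds for every visit that uses the option as written.

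**2. Clock-time examples.** With home dosing at hour H and a visit the next day at hour V, elapsed time = 24 − (H − V).
- H = 12:00, V = 09:00: 24 − 3 = 21 h, on-site dosing.
- H = 14:00, V = 09:00: 24 − 5 = 19 h, off-site option.
- H = 20:00, V = 09:00: 24 − 11 = 13 h, off-site option.

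The last case can also arise at Week 12. Dosing ends on Day 84 and the sample is due on Day 85, so a participant who dosed at 20:00 on Day 84 and is seen at 09:00 is sampled at 13 h.

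**3. Size per sample (illustrative).** Protocol 5.1, criterion 7a, equates 2 days with 5 terminal half-lives: 48 / 5 = 9.6 h. Assuming log-linear decline, the ratio to the 24 h value is 2^((24 − T) / half-life). The 4 h and 12 h half-lives are assumptions to show the range.

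| Draw time T | Half-life 9.6 h | Half-life 12 h | Half-life 4 h |
|---|---|---|---|
| 20 h (limit) | 2^(4/9.6) = 1.33 | 1.26 | 2.0 |
| 19 h | 2^(5/9.6) = 1.43 | 1.33 | 2.38 |
| 18 h | 2^(6/9.6) = 1.54 | 1.41 | 2.83 |
| 16 h | 2^(8/9.6) = 1.78 | 1.59 | 4.0 |
| 14 h | 2^(10/9.6) = 2.06 | 1.78 | 5.66 |

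**4. Size per visit summary (illustrative).** The share of off-site visits is not given. Assume 4 of 14 active participants are affected. The geometric mean is then inflated by ratio^(4/14):
- all four at 14 h: 2.06^(4/14) = 1.23;
- all four at 18 h: 1.54^(4/14) = 1.13.

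A slope on log trough shrinks by s² / (s² + p(1 − p)d²), with p = 4/14, d = ln(ratio) and an assumed between-participant log SD of s = 0.5:
- at 14 h: 0.25 / (0.25 + 0.204 × 0.521) = 0.70;
- at 18 h: 0.25 / (0.25 + 0.204 × 0.188) = 0.87.

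**5. Can time since dose be recovered?** At an off-site visit, the dose time that Section 6.3 expressly sends to the CRF belongs to the dose taken after the sample. The dose that determines the concentration is the preceding home dose. Its time is on the diary card, and the site needs it to apply the 20 h test. With the recorded draw time, time since dose can be derived from source. What is missing is a rule that puts the preceding dose time in the CRF for routine PK samples and uses it in the analysis.

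**The case against.** **The data are not lost.** A reader might infer that the CRF captures the wrong dose time and the error therefore cannot be corrected. The documents do not support that. Section 6.3 says what must be entered; it does not say the preceding dose time is left out. The diary holds that time. The CRF itself is not available here, sampling details are left to the SRM, and the SAP introduction leaves data handling conventions to the OPS. Any of these might already deal with the point. This objection stands, and it narrows the finding to a missing requirement in the protocol and SAP.

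**The size may be small.** The first dose is given at the site and dosing is meant to stay near the same time each day, which ties most participants to clinic hours. Neither document defines a trough window, and a draw just under 20 h differs little from one just over it. A 14 h sample at a 09:00 visit needs a 19:00 home dose. The 4-of-14 share, the log SD and log-linear decline for a modified-release tablet are all assumptions. This also stands: the 23% inflation and 0.70 slope are illustrations, not estimates for this trial.

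**Little depends on it.** The 15-fold trough rationale predates these samples. The decision criteria that SAP Table 2 names for the interim concern PASI75. The trough-PASI modelling is conditional on the data and sits outside the CSR delivery. Blood target engagement is sampled at the same visits as PK, so that plot is less affected. A reader might infer a threat to the efficacy result or to the dose rationale; there is none. The sole PK endpoint, its by-visit summaries and PK-predicted target engagement remain affected.

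**Conclusion.** The point holds. Under the protocol's own rule, every compliant off-site visit at Week 2, 4 or 8 gives a PK sample drawn less than 20 h after the previous dose. The endpoint and SAP 5.5 and 5.5.1 nevertheless treat it as a trough, with no window, flag or exclusion. That deduction needs no assumption beyond compliance.

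The direction of the error is upward. Its size rests on a half-life of about 9.6 h and log-linear decline: roughly 1.3-fold at 20 h and 1.8-fold at 16 h. The effect on the group summaries cannot be estimated because the share of off-site visits is not stated. No primary or secondary efficacy analysis is affected. The change is worth making because, followed as written, the plan biases its only PK endpoint, and the data needed to prevent this are already collected at source.

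It would be tempting to take 20 h as the trough cut-off. The documents use that figure only to define overdose and give no PK reason for it as a sampling window.

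**What to change.** **Protocol 8.5.1 and 6.3.** Require the CRF to hold the date and time of the last dose taken before each PK draw, in the terms already used in Appendix 6 note 5, at all PK visits including Week 12.

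**SAP 5.5 and 5.5.1.** Derive actual time since dose for every PK sample. Pre-specify one trough window, justified on PK grounds, and apply it alike at Weeks 2, 4, 8 and 12. List samples outside it and plot them by actual time since dose. Leave them out of the by-visit trough summaries, PK-predicted target engagement and trough-response plots. If the SRM, CRF or OPS already contains such a rule, a cross-reference is enough.

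**Cost.** One CRF field, transcribed from the diary card, and a few lines in the SAP. Some by-visit summaries will rest on fewer values. No change to dosing or visits is proposed.
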